13.0 APPENDICES

Appendix 1 - RD-X19 Investigational Device Manual (Instructions for Use)

# CHANGE CONTROL

Date	Details	Made By:	Against version
120CT23	Initial version	JB	N/A
24MAR24	Added secondary, sensitivity, supportive and exploratory analyses for the primary and key secondary endpoint.	JB	1.0

# Section 1. ABBREVIATIONS & DEFINITIONS

#### **ABBREVIATIONS**

ANCO'	VA	Analysis of covariance	
ATC	Anatomical therapeutic chemical		
BMI	Body mass index		
BRFS	Baseli	ne risk factor score	
CI	Confic	lence interval	
CRF	Case r	eport form	
DCT	Decentralized clinical trial		
DR-TE	AE	Device-related treatment-emergent adverse event	
DR-TE	SAE	Device-related treatment-emergent serious adverse event	
ET	Early t	ermination	
FAS	Full analysis set		
FDA	Food and Drug Administration (USFDA)		
GCP	Good Clinical Practice		
ICH	International Council for Harmonisation		
LOD	Limit of detection		
Ltd	Limited		
LLOQ	Lower	limit of quantification	
MedD	RA	Medical Dictionary for Regulatory Affairs	
NPAN	COVA	Non-parametric ANCOVA	
PH	Propo	rtional hazards	
PI	Princip	pal investigator	
PP	Per protocol		

- PT Preferred term
- RR Respiration rate
- SAE Serious adverse event
- SAP Statistical Analysis Plan
- SOC System organ class
- SOP Standard operating procedure
- SpO2 Oxygen saturation
- TEAE Treatment emergent adverse event
- TESAE Treatment emergent serious adverse event
- ULOQ Upper limit of quantification

# Section 2. INTRODUCTION & TERMS

## 2.1. INTRODUCTION

This document describes the statistical analysis and reporting plan for data from *A Randomized, Double-Blind, Sham Controlled, Stratified, Pivotal Efficacy and Safety Study of the EmitBio RD-X19 Treatment Device in Individuals 40 Years of Age and Older with Mild COVID-19 in the At-Home Setting* [1].The primary goal of the study is to evaluate the safety and efficacy of the RD-X19 treatment device to provide sufficient evidence to FDA to justify the authorization and/or approval of the device for treatment of subjects with mild COVID-19, age 40 and older in the home setting.

As described in the ICH E9 guidelines [2], [3] the purpose of this document is to provide a more technical and detailed elaboration of the principal features of the analysis described in the study protocol [1], and to include detailed procedures for executing the statistical analysis of the primary and secondary variables and other data.

Details of the procedures that will be followed by Quantics when undertaking data receipt, analysis and reporting are described in Quantics SOPs [4] and [5].

Any amendments to the SAP will be made prior to database lock.

Any additional analyses not described in the final SAP or deviations from the final SAP will be documented in the clinical study report.

Quantics Consulting Limited will perform the statistical analyses and are responsible for the production and quality control of all tables, listings, and figures.

# Section 3. STUDY OBJECTIVES AND DESIGN

### **3.1. Study Objectives**

The primary goal of the study is to establish the efficacy and safety of the RD-X19 light dosing treatment device to treat eligible subjects who have mild COVID-19 (based on the NIH and FDA definition of mild COVID-19) with sufficient data to support a regulatory filing for authorization and approval by FDA. Specifically:

□ Safety objective:

• To assess device-related Serious Adverse Events (SAEs) and Treatment Emergent Adverse Events (TEAEs), including local site reactions.

□ Effectiveness objectives:

- To assess the reduction in time to sustained resolution of COVID-19 signs and symptoms (without subsequent symptom recurrence or disease progression until the end of the study) with the RD-X19 device compared with a sham device.
- To assess the reduction in time to the first of two consecutive negative SARS-CoV-2 antigen tests (without subsequent virological rebound during the subjects' remaining time on study) when using the RD-X19 device compared with a sham device.

#### 3.2. STUDY DESIGN

This is a randomized, double blind, sham controlled study of the EmitBio RD-X19 light dosing treatment device. 326 subjects will be randomized at a 1:1 ratio into RD-X19 treatment and sham device treatment groups.

Subjects will be aged 40-years-old or over on the date of enrollment, have a positive COVID-19 test with time since symptom onset of 72 hours or less, and meet the NIH and FDA definition of mild COVID-19. For randomization, subjects will be stratified by age (categories 40-49 years and  $\geq$ 50 years) and baseline disease severity score (< 1.25,  $\geq$  1.25).

Subjects will be treated for 7 days and followed up for a further 7 days after the end of treatment (i.e., subjects will spend 14 days on the study in total).

#### **3.3.** DETERMINATION OF SAMPLE SIZE

The sample size was based on the primary end point of time to sustained symptom resolution. In the EB-P20-01 trial, for subjects aged 40-years-old or over with mild disease (based on the NIH and FDA definition of mild COVID-19), the hazard ratio for this endpoint in

<sup>1 The COVID-19 Composite Severity Score at baseline is defined as the sum of the eight individual COVID-19 symptom severity scores divided by eight.

the full analysis set (FAS) was 0.62. Assuming an overall (one-sided) type 1 error of 0.025, a total of 228 events for the primary endpoint gives 95% power for a hazard ratio of 0.62 and also gives 90% power for a hazard ratio of 0.65, as well as 80% power for a hazard ratio of 0.69.

A total of 326 subjects will be initially randomized 1:1 (to RD-X19 and Sham) which will result in approximately 228 events assuming that 90% of RD-X19 subjects and 50% of Sham subjects will have the event.

A blinded sample size review will be carried out by an independent statistician based on the first 164 randomized subjects, with the objective of seeing whether the sample size needs to be increased. See Section 8.1 for details.

### 3.4. STUDY VISITS

**Baseline visit:** Subjects will be screened, enrolled and randomized at the baseline visit on study day 1. Objective clinical assessments (vital signs, a complete physical exam, oropharyngeal exams) will be made by study staff.

**Daily days 1 to 7**: Study subjects will self-administer treatment twice daily, 5 minutes per treatment for 7 consecutive days. They will also self-assess for nine pre-specified COVID-19 sign and symptoms, perform a SARS-CoV-2 rapid antigen test and measure oxygen saturation twice a day, recorded using an e-diary. TEAEs will be ascertained (both solicited and unsolicited) by study staff during clinical site visits. While not specifically queried by the IQVIA decentralized clinical team members during a tele-visit, study subjects may report a treatment-emergent adverse event (TEAE) during the televisit or by contacting the clinical site at any time. DCT staff will make personal contact with study participants (via tele-visit) twice a day on each of these first seven days in order to ensure compliance with the treatment, SARS-CoV-2 rapid antigen testing, COVID-19 symptom severity scoring and measurement of oral temperature and oxygen saturation (SpO2). Subjects will return to the clinical site on study day 5(+/-1), or for early termination, for assessment by study staff and principal investigator (PI) or an appropriately credentialed delegated sub-investigator.

**Daily days 7 to 14:** No treatment but e-diary entries continue. Study staff will make personal contact with study participants, as required, to ensure all study procedures are completed. Study subjects will return to the clinical site on study days 8(+/-1) and 14(+/-2), or for early termination, for assessment by study staff and PI or an appropriately credentialed delegated sub-investigator. There must be a minimum of 48 hours between Day 5 and Day 8 clinic visits.

# Section 4. STUDY ENDPOINTS

## 4.1. PRIMARY ENDPOINT

The primary endpoint is the time to sustained resolution of COVID-19 signs and symptoms without subsequent symptom recurrence or disease progression (until the end of the study), measured in hours from time of randomization.

The first step in derivation of the primary endpoint is via the twice-daily assessments where the subject records signs and symptoms in the e-diary. Each of the eight symptoms (cough, sore throat, nasal congestion, headache, chills and/or sweats, myalgia, fatigue, and nausea (with or without vomiting) are classified as one of:

None (Grade 0)	Symptom not present
Mild (Grade 1)	No influence on daily activities
Moderate (Grade2)	Noticeable influence on daily activities
Severe (Grade 3)	Daily activities not possible

The single sign incorporated in the first step in derivation of the primary endpoint (see below) is whether or not oral temperature is greater than or equal to 100.5°F.

Note: Inclusion criterion 3 for the study requires that subjects have at least two moderate or greater for the eight symptoms, or one moderate or greater for these symptoms and fever (temperature ≥ 100.5°F).

In addition, oral temperature and oxygen saturation (SpO2) are self-measured twice daily by subjects and recorded in the e-diary. Each is measured three times (over 10 minutes); the analysis quantity will be the mean of these repeated measures. If fewer than three repeated measures are taken on a given occasion, the analysis quantity continues to be their mean. Respiration rate (RR) is measured on clinic visit days.

Note: For the first assessment, information to make the below classifications is collected twice, once as part of the baseline visit and once self-reported in the subject's e-diary. When classifying subjects for this timepoint, use the information collected as part of the baseline visit (CRFs: 'Covid-19 testing and symptoms' and 'Vital signs')

Based on this, each timepoint/assessment can then be classified in the following manner:

- Success (S) corresponds to resolution i.e. if all of the eight symptoms are graded with a severity score of 0 (absent) or 1 (mild), and the subject's oral temperature < 100.5°F.

- ii. Failure ( $F_n$ ) corresponds to  $n \ge 1$  of the nine signs and symptoms not meeting the condition described in (i) above.

- iii. Disease progression (D) corresponds to the subject having respiration rate (RR) ≥ 20/min and SpO2 < 96%. Both measures are based on the average of three replicate assessments over a 10-minute period. Additionally, disease progression will be classified as having occurred if pulmonary imaging demonstrates COVID-19 pneumonia based on an attended medical visit recorded on a medically-attended visit CRF or an AE/SAE report.

- iv. **Missing (M)** corresponds to the subject not recording all sign and symptom entries in their e-diary at this timepoint.
- Note: At baseline a subject would be  $"F_n"$  with  $n \ge 2$ , unless a subject did not satisfy inclusion criterion #3.

For subjects with sign/symptom data missing at a particular timepoint, data handling rules are as follows.

- (1) Subjects who do not input data for any signs or symptoms at a particular assessment will be assigned code "M" (missing) at that assessment, as described above.
- (2) Subjects who input data for some but not all signs and symptoms at a particular assessment will be handled as follows:
  - a. If *any* of the signs and symptoms for which data was provided *do not* meet the resolution condition described in (i) above, then the subject will be assigned code  $F_n$  (failure to achieve symptom resolution for "n" of the 9 signs and symptoms) at this timepoint.
  - b. Otherwise, if data was recorded for at least 6 of the 9 signs and symptoms and all meet the resolution condition described in (i) above, then the subject will be assigned code "S" (success).
  - c. Otherwise, if fewer than 6 of the 9 signs and symptoms have data recorded then the subject will be assigned code "M" (missing).

The primary endpoint is defined as the time in hours from the time of randomization to the time of the first "S" in a sequence of 5 "SSSSS" for which there is no subsequent symptom recurrence or disease progression during the subjects' remaining time on study. A maximum of one intermediate "M" is allowed within a sequence of at least 5 consecutive "S" values to also qualify as sustained resolution, i.e., "SMSSSS", "SSMSSS". "SSSMSS", and "SSSSMS" would each be counted as sustained resolution.

Note: Only timepoints after the time of randomization are considered when determining if the primary endpoint has been met.

After sustained resolution is achieved, **symptom recurrence** is defined as having three or more consecutive assessment times (corresponding to an approximately 24-hour period) where *two* or more of the nine sign and symptoms do not meet the resolution condition in (i). Any number of intermediate assessment times with M (missing) between the assessment

times with  $F_n$  (failure to resolve) where  $n \ge 2$  symptoms or signs, does not prevent the subject from being classified as having experienced symptom recurrence.

A subject is defined to have had **disease progression** when they record "D" (disease progression) as defined in section 4.1(iii).

Note: A subject that has symptom recurrence and/or disease progression is still eligible to have the event for the primary endpoint later; if they subsequently have five consecutive assessments at which the signs and symptoms have resolved ("SSSSS"), but with no subsequent recurrence or disease progression during the subjects' remaining time on study.

### 4.2. KEY SECONDARY ENDPOINT

Note that at each of the twice-daily assessment times at which the subject is scheduled to take the SARS-CoV-2 antigen test, the results will be either Negative (N), Positive (P), Inconclusive (I), or Missing (M).

The key secondary endpoint is the **time to first of two consecutive negative SARS-CoV-2 antigen tests** (with a minimum time between tests of 6 hours) without subsequent virological rebound during the subject's remaining time on study. It is measured in hours from the time of randomization to the time of the first of two consecutive negative tests.

The following sequences will be counted as satisfying this condition of having "two consecutive negative SARS-CoV-2 antigen tests":

- a) "NN" and the two tests are at least six hours apart.
- b) More than two consecutive "N" values where the first and last are at least six hours apart.
- c) "N" followed by at most three "M" or "I" values, followed by "N" where the two "N" values are at least six hours apart.

In the remainder of the SAP the use of "NN" will refer to any of cases (a)-(c).

Note: Only tests taking place after the time of randomization are considered when determining if the key secondary endpoint has been met.

**Subsequent virological rebound** is defined as having two or more positive tests out of three consecutive assessments. In addition to "PP", the following test result patterns, seen after one of (a) to (c) above, will be sufficient to define subsequent virological rebound:

- i. "PPP"
- ii. "PPN"
- iii. "PNP"
- iv. "NPP"

Note: If a "P" is followed by an "M" or "I" then the "P" will be carried forward so that this will also be counted as a subsequent virological rebound.

#### 4.3. SECONDARY QUALITATIVE MEASURES

The following are secondary qualitative measures (each taking the values yes, no) recorded at the post-baseline clinic visits for COVID-related assessment:

- Loss of taste
- Loss of smell
- In the past 24 hours, have you returned to your usual health (before your COVID-19 illness)?
- In the past 24 hours, have you returned to your usual activities (before your COVID-19 illness)?

## 4.4. SAFETY ENDPOINTS

The safety analysis will consider all TEAEs whether solicited (as part of the reactogenicity assessments including oropharyngeal assessment) or unsolicited.

In addition to TEAEs, the following safety endpoints will be assessed:

- o Concomitant medications and therapies
- o Vital signs
- o Physical examination

# Section 5. ANALYSIS POPULATIONS

The study uses three analysis populations which are defined below.

The treatment to which an individual is randomized should be determined using the answer to the question 'Randomization outcome' in the 'Randomization Assignment' CRF.

The treatment an individual actually received is to be determined by cross-referencing the 'Device ID' field in the 'RD-X19 Device Collection' with a list of which devices are active and which are sham.

# 5.1. FULL ANALYSIS SET (FAS)

The Full Analysis Set (FAS) will consist of the set of randomized subjects, excluding: (i) subjects who were mis-randomized; and (ii) subject IDs corresponding to study participants that were re-randomized under a different subject ID.

This population will be the primary analysis population for all efficacy endpoints. Subjects will be analyzed on the basis of the treatment to which they were randomized, regardless of what treatment they actually received.

## 5.2. SAFETY POPULATION

The safety population will consist of all randomized subjects who received any study treatment. Subjects will be analyzed on the basis of the treatment that they received.

This population will be the primary analysis population for all safety analyses.

## 5.3. PER PROTOCOL (PP) POPULATION

The Per Protocol (PP) Population will exclude from the FAS study subjects who experienced one or more of a pre-specified subset of major protocol deviations/violations, as well as subjects who did not meet certain pre-specified criteria concerning number of treatments received. The list of reasons for excluding subjects from the PP population is:

- 1. Subject received the wrong treatment
- 2. Subject not positive for COVID-19 based on qPCR
- 3. Did not satisfy Inclusion criteria #1, #3, and/or #4
- 4. Satisfied exclusion criteria #2 and/or #4
- 5. Number of treatments received was < 7
- 6. After randomization received one or more FDA-approved medications for COVID-19 treatment.

Subjects who did not satisfy any of #1-#4 above and received at least one treatment, but who only first satisfied #6 after visiting Urgent Care, visiting the Emergency Room, or after hospitalization will not be excluded from the PP population.

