treatment, or which are present prior to treatment initiation but which increase in severity after treatment. No AEs that are not TEAEs are expected in this study since the time between enrollmen t and first treatment is very brief. TEAEs will be determined by self-assessment and reported to decentralized team members during televisits. These unsolicited TEAEs will be reported by the decentralized team members to the clinical site staff. TEAEs will also be captured objectively by clinic staff during physical and oropharyngeal examinations on study days 5, 8 and 14, or during early termination. Volunteers will be instructed to contact designated clinical trial staff for TEAEs of a medically-urgent nature as soon as is practically possible and to seek immediate medical care, if needed. Study subjects who experience progression of disease to moderate severity will be instructed to seek care from their primary care provider or an urgent care center and will be advised to request a pulmonary imaging study (preferrably CT) as part of their healthcare evaluation to document the presence and extent, or absence, of COVID-19 pneumonia. Study subjects who progress to severe disease will be instructed to seek urgent medical care at their nearest Emergency Department. All study subjects who require a medically-attended visit will be asked to provide the results of their evaluations to study staff to assess whether COVID-19 progression has occurred. Study subjects who are hospitalized will be tracked to assess the date and time of hospital admission to discharge or death and these events will be captured as part of the trial data.

Previous clinical trials of RD-X19 have demonstrated very infrequent, transient and mild devicerelated TEAEs. In the unexpected event that device-related SAEs or patterns of device-related TEAEs are observed, the Sponsor's Medical Monitor/Chief Medical Officer will immediately consult with and refer these data to the Independent Medical Monitor for review and recommendations.

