4.6.2 Exclusion Criteria

A subject with any of the following criteria will be excluded from participation in this study:

- 1. Positive for Influenza A and B antigen using an FDA-authorized rapid diagnostic test.
- 2. Individuals < age 40 on study day 1.
- 3. Individuals who are symptomatic for COVID-19 for more than 72 hours on study day 1.
- 4. COVID-19 signs associated with moderate or greater disease with evidence of lower respiratory involvement including shortness of breath (SOB) at rest or as determined by an exertional SOB protocol, SpO2 ≤94, respiratory rate ≥20 breaths per minute, heart rate ≥90 beats per minute, or abnormal pulmonary imaging.
- 5. Any medical disease or condition that, in the opinion of the site Principal Investigator (PI) or appropriate sub-investigator, precludes study participation.
- 6. History of use of a rescue inhaler for uncontrolled asthma within one month of study day 1.
- 7. History of recurrent alcohol intoxication or other recreational drug use (excluding medically prescribed cannabis) within one month of study day 1.
- 8. History of use, within one month of study day 1, of any FDA-authorized treatment for COVID-19. Use of non-approved putative therapies for COVID-19 (hyroxycholorquine, ivermectin, azithromycin) must be discontinued prior to enrollment in the study.
- 9. History of any systemic antiviral therapies within one month of study day 1.
- 10. History of oral or parenteral corticosteroid use within one month of study day 1. Active use of nasal or inhalable steroids is also exclusionary. Topical steroids are not exclusionary.
- 11. History of any chronic medical condition that has required adjustments to the type, dose or schedule of medical treatments within one month of study day 1.
- 12. Requirement to use narcotic medication for analgesia.
- 13. History of vasomotor rhinitis with or without post-nasal drip within one month of study day 1.
- 14. History of hypersensitivity or severe allergic reaction (e.g., anaphylaxis, generalized urticaria, angioedema, other significant reaction) to sun exposure.

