- 3) Those who progress to moderate disease indicated by new onset shortness of breath (respiratory rate ≥20/minute) and SpO2 of < 96% confirmed by pulmonary imaging or lower airway disease diagnosed by pulmonary imaging involving < 50% of lung parenchyma;

- Those who progress to severe disease with respiratory rate >30/minute and/or O2 saturation ≤93% on room air or lower airway disease confirmed by pulmonary imaging involving ≥ 50% of lung parenchyma;
- 5) Those who require hospitalization for severe COVID-19;
- 6) Those who require endotracheal ventilation or ECMO with or without the use of solumedrol; and
- 7) Those who die.
- Subjects with a primary care, urgent care, or emergency room visit that are not hospitalized as a result of their medical consultation, may continue treatment with the investigational device and should attend regularly scheduled follow up visits per protocol. Subjects that are admitted to the hospital should discontinue all treatment in lieu of standard of care for severe/critical COVID-19 illness or other SAEs. Such subjects' endpoint data will be right censored as specified in the Statistical Analysis Plan (SAP).
 - Subjects who are treated with any FDA-authorized COVID-19 therapy will discontinue treatment but will continue to be followed per protocol. Such subjects' endpoint data will be right censored as specified in SAP.
 - Subjects who first reach clinical resolution on or after study day 11 should be scheduled for their day 14 visit, which has a +/- 2 day window, so that a total of five consecutive visits (including the first resolution visit) are captured where resolution *may* be observed thus allowing the primary clinical sustained resolution endpoint to be met. Under no circumstances, however, may a study subject be scheduled for their day 14 visit beyond study day 16.

	Page 46 of 70
EmitBio Inc.	Version: 3.1
EB-P30-01	7 February 2024

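### The Per Protocol exemption in SAP 5.3 omits primary care and waives the minimum-treatment rule only for subjects given a COVID-19 medicine, so equally compliant subjects are classified oppositely

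*SAP*

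**What the plan says.** SAP 5.3 lists six reasons for removing a subject from the PP population. Two matter here. Reason #5 is "Number of treatments received was < 7". Reason #6 is "After randomization received one or more FDA-approved medications for COVID-19 treatment". A closing paragraph sets an exemption. It starts with "Subjects who did not satisfy any of #1-#4 above and received at least one treatment" and continues "but who only first satisfied #6 after visiting Urgent Care, visiting the Emergency Room, or after hospitalization will not be excluded". Reason #5 is not among the conditions that block the exemption, so a subject it covers is kept even with fewer than 7 treatments.

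The protocol directs the same subjects as follows:

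- Section 4.3: those who progress to moderate disease "will be instructed to seek care from their primary care provider or an urgent care center".
- Section 8.6 names primary care, urgent care and emergency room visits together, and lets subjects who are not admitted after such a visit continue the device.
- Section 8.6 also states: "Subjects that are admitted to the hospital should discontinue all treatment". It separately instructs subjects given an FDA-authorized COVID-19 therapy to stop the device and remain in follow-up.
- Section 8.1.3 accepts authorized therapy as proper care for progressed disease.

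SAP 8.2.4 and 8.3.2 run PP analyses of the primary and key secondary endpoints and call them supportive. SAP 7.2 tabulates PP exclusions using the same list of reasons.

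**The concern.** The exemption shows that the SAP means to keep subjects whose COVID-19 medicine came through medical care for worsening illness. As worded, it does this for some of them only. What separates those kept from those dropped is the clinic they attended or, after hospital admission, whether a particular class of medicine was given. Neither measures adherence to the protocol.

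Both exclusions follow from an event after randomization that signals a poor course. If the device changes how often subjects progress, the numbers removed will differ by arm, and the PP comparison then partly reflects that selection. The PP analyses are meant to show the effect in subjects who used the device as directed, and these subjects did follow their instructions.

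**Working it through.** No figure in the plan has to be reproduced, because the issue is the logic of the rule. I applied SAP 5.3 literally to pairs of subjects who differ in one respect. Every subject is clear of reasons #1 to #4 and has had at least one treatment. I take the SAP's FDA-approved and the protocol's FDA-authorized to mean the same medicines.

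| Subject | Treatments | Reasons met | Exempt? | PP |
|---|---|---|---|---|
| Progressor, primary care, COVID-19 medicine | 8 | #6 | No, setting not listed | Dropped |
| Same, urgent care or emergency room | 8 | #6 | Yes | Kept |
| Progressor, primary care, COVID-19 medicine | 4 | #5, #6 | No, setting not listed | Dropped |
| Same, urgent care | 4 | #5, #6 | Yes | Kept |
| Admitted to hospital, COVID-19 medicine given | 4 | #5, #6 | Yes | Kept |
| Admitted to hospital, no such medicine | 4 | #5 | No, #6 never met | Dropped |

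**When reason #5 applies.** On the standard schedule, treatments completed by the end of Day d number 2d: 2, 4 and 6 on Days 1 to 3. The 7th is the first treatment of Day 4. On the split schedule (Protocol 8.3.1) the count is 2d − 1: 1, 3 and 5, and the 7th falls on Day 4 PM. A stop because of admission through Day 3, or on Day 4 before that treatment, leaves the subject below 7.

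**What each exclusion removes from the analysis.**

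- Hospitalized subjects: SAP 8.2 rule I (primary endpoint) and SAP 8.3.1 rule i (key secondary) both censor at 360 hours. Each one dropped is a subject carried as unresolved for the whole follow-up.
- Primary care subjects, primary endpoint: under SAP 8.2 rule III, a user of nirmatrelvir/ritonavir or molnupiravir who had not already met the endpoint is censored when the drug starts. The exclusion removes a shorter, censored record, not a 360-hour one.
- Primary care subjects, key secondary endpoint: SAP 8.3.1 rule i censors subjects who progress or require authorized therapy at 360 hours, so here the exclusion does remove a full-length non-event.

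**Number affected.** The planned arm size is 326 / 2 = 163, so each 1% of an arm is 1.63 subjects. The documents give no rate for rescue through primary care. If one assumes 2% to 5%, the count is 0.02 × 163 = 3.3 to 0.05 × 163 = 8.2 per arm. That range has no source. The nearest information is the earlier 31-subject trial described in Protocol 4.1, where nobody needed medical intervention beyond over-the-counter remedies. For admission before treatment 7 without a COVID-19 medicine there is no basis for even an assumed rate.

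**The case against.** **Little depends on the PP population.** Both endpoints are tested on the FAS, and no alpha is spent on the PP analyses. SAP 8.2.5 adds a FAS sensitivity analysis of the primary endpoint that holds hospitalized, progressed and treated subjects as unresolved to 360 hours. SAP 7.2 will show exclusions by reason and arm, so an imbalance would be visible. All of this stands and limits the importance of the point.

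**Reason #5 is a minimum-exposure rule.** Protocol 9.3 provides for criteria on the number of treatments separately from deviations, so dropping low exposure whatever its cause would be defensible. That would answer the hospital case if the SAP applied it throughout. It does not: the exemption keeps a subject admitted after 4 treatments when a COVID-19 medicine was given. The inconsistency is inside SAP 5.3. Device stops under Protocol 7.5.1 also meet #5, but no exemption reaches them, so no like pair is split.

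**Three stronger readings are tempting, and the documents do not support them.**

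- A reader might infer that anyone who stops the device on instruction is dropped. Subjects who meet #6 after urgent care, the emergency room or admission are kept, even below 7 treatments.
- A reader might infer that the list is deficient because the only exclusion-criterion reason is "Satisfied exclusion criteria #2 and/or #4", so that breaches of exclusion criteria #8 to #10, such as "History of any systemic antiviral therapies within one month of study day 1", stay in. Protocol 9.3 allows a chosen subset of major deviations. These breaches precede randomization and create no post-randomization selection, and anyone given an FDA-approved COVID-19 medicine after randomization is caught by #6. Which eligibility breaches to carry into PP is a choice the protocol leaves open.
- A reader might infer a tilt toward the device. Nothing shows one. If the device reduced progression, more of the dropped 360-hour records would come from the sham arm, which would shrink the PP difference.

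**Conclusion.** The point holds in two parts. SAP 5.3 classifies equally compliant progressors oppositely by care setting, because primary care is missing from the exemption. It also classifies subjects admitted before the 7th treatment oppositely according to whether an FDA-approved COVID-19 medicine was given, because the waiver of #5 depends on #6. Both are outcome-driven exclusions.

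The consequence is confined to the supportive PP analyses of the two endpoints; the FAS results cannot change. The number of subjects is unknown and probably small. For the primary endpoint, the hospital case removes 360-hour records, while the primary care case mainly removes records censored at drug start. The conclusion rests on a literal reading of the exemption and on treating approved and authorized as the same medicines. It is worth correcting because the correction is easy and the rule defeats its own evident purpose.

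**What to change.** Amend the closing paragraph of SAP 5.3, and align the matching list in SAP 7.2:

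1. Add a primary care visit, or any other medically attended visit for COVID-19 progression, to the settings after which a subject who first meets #6 is kept.
2. For subjects clear of #1 to #4 with at least one treatment, do not apply #5 when treatment stopped because of hospital admission, whether or not #6 is met.

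Do not widen the second item to everyone who stopped the device because of authorized COVID-19 therapy. Protocol 8.6 gives that instruction to every such subject, so the wider waiver would all but empty #6 and would keep subjects who took an antiviral without progression or a care visit.

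The change affects analysis-set membership only and alters no clinical instruction. It costs a few lines of SAP text, made before unblinding (Protocol 9.3) and before database lock (SAP 2.1). The inputs are already planned: a medically-attended-visit CRF (SAP 4.1), hospitalization as an action on the AE CRF (SAP 8.5.3) and the treatment count (SAP 8.5.1). The existing exemption already requires the care setting to be known; the sponsor should confirm that primary care visits can be identified in the same records.
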